5.5.2 EKG

EKG will be taken by an outside pediatric cardiologist.

- Patients who are screened and those who participate in this study will have appointments made for them by the Investigator or his study staff with the cardiologist associated with the study site.
- All required EKG appointments will be made upon the accrual of a patient into this trial and that information will be provided to the caregiver in writing.
- Detailed instructions will be provided to the caregiver regarding the directions to the cardiologist's office, contact information, times of the appointments, and it will be confirmed that these EKG appointments are an essential part of the study and all visits must be made at the scheduled times.
- The Investigator and/or the study staff will be responsible for obtaining the results of these EKG and entering them into the database prior to the next scheduled study visit.
- EKG will be taken as part of the baseline screening procedure for the Assigned Dosage Group patients (Groups 1 & 3).

- Patients in the Assigned Dosage Groups will have a repeat EKG taken within 3 days prior to the Week 1, 2, 3, and 4 treatment interval visits as well as at the 1 week 4 week post dosing follow-up visits.
- EKG will be taken as necessary in any patient who manifests a potential cardiovascular AE in response to L1-79 such as tachycardia or bradycardia.
- In the event that 2 or more cardiovascular AE are reported in a group additional EKG may be warranted and a determination will be made as to the proper course of action at that time.

5.6 Clinical Evaluation

The purpose of this study is to assess the safety and efficacy of L1-79 in the treatment of autism. To that end, certain clinical evaluations (including physical examination, vital signs, and laboratory tests as described above) will be performed during different scheduled clinic visits.

5.7 Psychometric Testing

The following assessment instruments will be used in this study:

- Vineland Adaptive Behavior Scale II (VABS II): Questionnaire (Sparrow, et al 2006)
- Aberrant Behavior Checklist and subscales: (Aman, MG & Singh, N. 1988)
- Clinical Global Impressions Scale, and subscales (Guy 1976)
- Autistic Diagnostic Observation Schedule (Western Psychological Services)
- Autism Diagnostic Interview – Revised (ADIR): Rutter et al 2003)
- Social Responsiveness Scale (SRS): (Constantino, J. 2007)
- Spense Anxiety Scale (SAS): (Spense, SH 1998)
- Repetitive Behavior Scale – Revised (RBS – R): (Lam, KS & Aman, MG 2007)

Additionally, clinical observations will be made regarding by the Investigator at each visit that should include factors such as:

- the subject's eye contact
- abnormal gestures
- response to having their name called
- ability to draw specified shapes
- interaction with toys or other objects

5.7.1 TESTING AT SCHEDULED CLINIC VISITS

The following events will occur at the scheduled clinic visits during the treatment phase of the protocol by the Investigator or the appointed study staff:

- Review of the submitted VABS II caregiver form,
- Conduct a physical (screening, visit 4, and follow up visits) and review the vital signs (all visits),
- Caregivers will be questioned about Adverse Events,
- If appropriate, medication will be returned or dispensed and the medication log completed.

- A CGI-I and CGI-S assessment will be made
- An ABC-C test will be completed
- A SRS form will be completed
- An RBS-R form will be completed
- Caregiver anecdotes will be solicited and recorded
- Patient interactions with Investigator and caregiver will be noted.

5.7.1.1 Pre- Post-Dosing testing

- An ADOS test will be administered as part of the screening procedure. The ADOS will be used as a secondary outcome measure and will be repeated just prior to the 4th weekly treatment visit.

5.8 Investigator Rating of Patient Response

The CGI-S (severity) form will be completed at on day 0, and at each weekly visit during the dosing phase of the study, and at the follow-up visit. The CGI-I (improvement) will be completed at each weekly treatment visit.

5.9 Schedule of Procedures

The evaluation schedule for the study is provided in Appendices A and B and described below.

5.9.1 ACCRUAL OF SUBJECTS INTO THE STUDY

Following an assessment of each patient for compliance with the inclusion and exclusion criteria described above, acceptable subjects will be enrolled in this study. The screening visit and all tests that are required at screening will be completed such that subjects will receive their first dose within 3 weeks of screening.

5.9.1.1 Entry into the study

- At the time all inclusion and exclusion criteria will have been evaluated and met, the patient will be accepted for enrollment. Patients will be assigned a study number and randomized to one of the four treatment groups. The initial two weeks of medication will be provided at the time of randomization.
- The caregiver for each patient will be given instructions as to their responsibilities and how to perform them, which includes:

5.9.1.2 Explanation of Caregivers Responsibilities

- The caregiver for each patient accepted into the study will have their responsibilities as detailed in the Study Compliance Agreement explained to them in detail. These responsibilities include:
 - To make sure the patient takes the assigned study medication according to the study schedule
 - To make sure the patient attends each clinic visit at the appropriate time
- To return all unused medication at the 2 and 4 week visits

5.9.1.3 Enrollment of Subjects (Day 0)

- Subjects who meet the inclusion and exclusion criteria for this study will be enrolled. They will be issued a study number based upon a random assignment of subjects to dosage groups in a blinded fashion using a code provided by the sponsor.
- For each screened patient a discrete file will be created.
- For screen failures, their files will contain the screening data that supports their failure to qualify for enrollment in the study.
- For patients that qualify for enrollment, their files will contain all documentation pertaining to that patient's participation in the study, including:
 - A fully executed consent form
 - An executed assent form
 - A fully executed caregiver compliance form
 - Copies of the patient history and all laboratory, physical, and electrocardiographic results,
 - Copies of all psychometric tests
 - Copies of all physician's notes on the patient's participation in the trial, including any information submitted by caregivers.
 - Any information provided by caregivers
- Consistent with GCP, study information will refer to subjects only by study number or initials. No subject names or other identifying information will be provided.

5.9.1.4 Off-Site Events

5.9.1.4.1 Electrocardiograms

All EKGs will be read by an independent pediatric cardiologist. An EKG will be as specified in section [5.5.2](#). The follow-up EKG must be taken within 1 week following the patient's last dose.

5.9.1.4.2 ADOS

ADOS testing will be performed by a certified ADOS test administrator immediately before the screening visit and immediately to the end of the 4 weeks of active dosing. The follow-up ADOS must be taken within 1 week following the patient's last dose.

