5.2 Drug Administration

5.2.1 THE L1-79 REGIMEN

Subjects will receive either 100 mg or 200 mg or matching placebo t.i.d. for a total of 28 days of dosing. The doses of L1-79 were determined based upon preliminary clinical research in subjects between 2½ and 24 years of age and doses between 90 and 200 mg t.i.d..

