5.9.2.6 Week 4 Visit (Study Day 28)

- ADOS (all patients) – to be performed during the last week of dosing while patients are still on medication
- Investigators will solicit any adverse events from the patient and/or caregiver and assess
- vital signs
- EKG, Blood and urine samples for PK analysis (Assigned Dosage Group patients only)
- Blood and urine samples for safety analysis for all patients
- Blood drawn for plasma for laboratory studies and for storage
- ASD assessments will be performed, including: ABC, SRS, RBS-R, VABS, CGI-S and CGI-I
- Question caregiver or patient about the patient's week, including questions regarding any changes in home life activities, events at school, sleep, or other matters germane to an understanding of the patient's autistic
- Record concomitant medications
- Record all adverse events

- Confirmation of medication administration and the collection, counting and logging of unused medicine

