6.1.5 EFFICACY ENDPOINTS

6.1.5.1 Main Efficacy Endpoint

The main endpoint will be based upon changes in the CGI, which shall be based on the aggregate of all testing as reviewed and interpreted by the Investigator. Comparisons between the different active treatment arms will be made, as will comparisons between the active treatment arms and the placebo arm.

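### The timing rules for the end-of-treatment ADOS contradict each other, so a secondary outcome could mix scores taken on drug with scores taken after dosing has stopped

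*Combined protocol and SAP*

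**What the plan says.** Four places in the protocol time the end-of-treatment ADOS.

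- **Section 5.9.1.4.2 (ADOS, under Off-Site Events)** has two sentences. The first places the test "immediately to the end of the 4 weeks of active dosing"; a word appears to be missing, but the sense points to the end of active dosing. The second is unambiguous: "The follow-up ADOS must be taken within 1 week following the" patient's last dose.
- **Section 5.9.2.6 (Week 4 Visit)** lists the ADOS for all patients, "to be performed during the last week of dosing while patients are still on medication".
- **Section 5.7.1.1** says that the test "will be repeated just prior to the 4th weekly treatment visit".
- **Appendix A** marks the ADOS at Screening and at Wk 4 (Day 28 ± 2). It marks none at the 1-week post-dosing visit or the 4-week follow-up.

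On its role, section 5.7.1.1 states: "The ADOS will be used as a secondary outcome measure". ADOS change is also named in the secondary objectives (2.2.2) and among the additional efficacy endpoints (3.2.2.2). The main efficacy endpoint is the CGI, "which shall be based on the aggregate of all testing as reviewed and interpreted by the Investigator" (6.1.5.1). CGI-S and CGI-I are both rated at the Week 4 visit (5.8, 5.9.2.6).

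**The concern.** A test required in the week after the last dose and a test required while the patient is still taking the drug are different measurements. Nothing in the protocol says which rule governs, so sites, or staff within a site, could reasonably act on different ones.

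Two things are at stake. First, the end-of-treatment ADOS could be an on-drug score for some patients and an off-drug score for others, with the split decided by which section was read and when an appointment was free. No second on-treatment ADOS exists in that phase to repair this. Second, an ADOS taken after the Week 4 visit cannot inform the CGI rated at that visit, so Week 4 ratings could rest on different information from one patient to the next.

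**Working it through.** The plan gives no power, effect size or standard deviation for the ADOS, so there is no figure to reproduce. The check is a comparison of windows with simple day arithmetic.

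**Inputs**
- Dosing: "for a total of 28 days of dosing" (5.2.1), first dose at Day 0. The last dose therefore falls on about Day 27 or 28, depending on how Day 0 is counted.
- Week 4 visit window: 28 ± 2, so Day 26 to Day 30 (Appendix A).
- Randomized patients: 10 per active dose (Synopsis).
- Offset time of any drug effect: not given.

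**Windows side by side**

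| Source | ADOS window | Days after last dose |
|---|---|---|
| 5.9.2.6 | last week of dosing, about Days 21–28 | 0 |
| 5.7.1.1 | just before the Week 4 visit | 0 if the visit is on time |
| Appendix A | Day 26–30 | 0, or a few days if the visit is on Day 29–30 |
| 5.9.1.4.2, last sentence | from the last dose to about Day 34–35 | up to 7 |

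The windows of 5.9.2.6 and the last sentence of 5.9.1.4.2 can at most touch on the day of the last dose. Otherwise, meeting one breaks the other.

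**Is it an additional test?** Appendix A schedules one post-baseline ADOS and none after Wk 4. The follow-up ADOS of 5.9.1.4.2 is therefore the end-of-treatment test. The rollover ADOS in Appendix B belongs to a separate open-label course.

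**Gap to the Week 4 CGI.** With the visit on Day 28 and the ADOS on Day 35, the ADOS comes 35 − 28 = 7 days after the rating. With the visit on Day 26, the gap is 35 − 26 = 9 days.

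**Effect on the ADOS comparison.** Let Δ be the on-drug active-placebo difference, f the share of active patients tested after their last dose, and w the share of the effect lost by then. The expected observed difference is Δ × (1 − f × w). Both f and w are assumptions:

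| | w = 0 | w = 0.5 | w = 1 |
|---|---|---|---|
| f = 0.25 | no loss | 12.5% loss | 25% loss |
| f = 0.5 | no loss | 25% loss | 50% loss |

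With 10 randomized patients per active dose, each late test adds 1/10 to f. One late patient therefore costs between 0% and 10% of that dose's expected difference, depending on w.

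**The case against.** The strongest reply is that one sentence is out of line and the rest of the protocol agrees. Sections 5.7.1.1 and 5.9.2.6, Appendix A and the first sentence of 5.9.1.4.2 all point to Week 4, and section 5.9.2 sends sites to Appendix A for visit events. The outlying sentence closely resembles the EKG sentence just above it in 5.9.1.4.1, so it may have been carried over (an inference). It could also be read as an outer deadline. This is fair as to the likely intent. It does not remove the problem, because the sentence is worded as mandatory and, even as a deadline, it admits off-drug testing.

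Some stronger readings are tempting, but the documents do not support them.

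- A reader might infer that a patient tested on Day 35 has fully complied. That test would breach 5.9.2.6 and the Appendix A window.
- A reader might count 7 days × 3 = 21 doses out of 28 × 3 = 84 and call it 25% missed treatment. The 28-day course is complete by then. These are drug-free days after it, and the ratio measures neither lost exposure nor lost effect.
- A reader might assume that sites book the ADOS from 5.9.1.4.2. No section says how it is booked; detailed booking instructions exist only for the EKG (5.5.2).
- A reader might conclude that the main efficacy endpoint as a whole is compromised. Section 6.1.5.1 does not name Week 4 as its time point. The CGI ratings at Weeks 1 to 3 have no new ADOS for anyone, and a late ADOS can still inform the Week 8 rating. Some incompleteness is also built in, since the Spence scale is not given at Week 4. Only the Week 4 rating is affected.

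**Conclusion.** The point holds as an internal inconsistency that should be reconciled. The single post-baseline ADOS of the main treatment phase has timing rules that cannot be followed together, apart from a possible coincidence on the last dosing day, and no section resolves them. Acting on the last sentence of 5.9.1.4.2 allows testing up to about 7 days after the last dose.

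That ADOS values could mix exposure states follows from the text alone. Dilution of the active-placebo difference is conditional: it needs some active patients to be tested late and some of the effect to be gone by then, and the documents fix neither quantity. If the effect persists for a week, there is no dilution. The possible absence of the ADOS from the Week 4 CGI does not depend on offset time.

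Section 6.1 plans descriptive statistics and acknowledges the lack of power, so no error rate or sample size is affected. With groups of 10, a few late tests could still visibly shift a group summary.

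**What to change.** Replace the last sentence of 5.9.1.4.2 and complete its first sentence, so that 5.9.1.4.2, 5.7.1.1, 5.9.2.6 and Appendix A all give one window: ADOS in the last week of dosing, on or before the day of the last dose, and before the Week 4 CGI is rated. Most of this is already the protocol's majority rule. The order relative to the CGI is only implied, by 5.7.1.1, and should be made explicit.

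Add a note to Appendix A that the +2 days of the Week 4 visit window do not extend the ADOS past the last dose. Without it, a test on Day 29 or 30 could still be off drug.

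Record the ADOS date and the last-dose date. In the analysis plan still to be written (6.1), flag any ADOS taken after the last dose and summarise it separately from on-treatment values.

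The cost is a short wording amendment, slightly tighter scheduling with the ADOS administrator, two dates to record and one analysis flag. No test or visit is added.

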5.9.2 SCHEDULED CLINIC VISITS – ALL PATIENTS

A listing of all events to be performed at each visit is presented in [Appendix A](#). All data will be recorded in the primary source documents and entered into the electronic database within 3 days of each patient visit.

5.9.2.1 Screening Visit

- Assessment of each patient for compliance with the inclusion and exclusion criteria described
- Demography and Medical History including blood-related family members
- Blood and urine samples for safety analysis
- Blood drawn for plasma for laboratory studies and for storage
- Physical Examination including vital signs
- ADOS test

- ADI-R administered by telephone
- All current medications will be recorded
- Once the patient has completed all screening assessments and all inclusion criteria have been met, the patient will be randomized

5.9.2.2 Day 0 Visit

- Subjects will be assigned a randomized study number from a list of study numbers based upon a blinded random assignment of subjects to dosage groups. This study number, consisting of a 2 digit site number and a 3 digit patient number (i.e. XX-YYY) will identify the patient and the drugs allotted to that patient.
- Vital signs
- ASD assessments will be performed, including: ABC, SAS, SRS, RBS-R, CGI-S, & VAB II questionnaire.
- Question caregiver or patient about the patient's week, including questions regarding any changes in home life activities, events at school, sleep, or other matters germane to an understanding of the patient's autistic presentation.
- Assigned Dosage Group patients will also have an EKG, PK and safety blood draws, & 24h urine sample taken prior to dosing, with an additional PK blood draw 1 hour post dosing
- Record concomitant medications
- Record all adverse events
- Dispense 2 weeks of medication

5.9.2.3 Week 1 Visit (Study Day 7)

- Vital signs
- ASD assessments will be performed, including: ABC, SRS, RBS-R, CGI-S, and CGI-I
- EKG, Blood and urine samples for PK analysis (Assigned Dosage Group patients only)
- Blood and urine samples for safety analysis (Assigned Dosage Group patients only)
- Question caregiver or patient about the patient's week, including questions regarding any changes in home life activities, events at school, sleep, or other matters germane to an understanding of the patient's autistic presentation.
- Confirmation of medication administration
- Record concomitant medications
- Record all adverse events

5.9.2.4 Week 2 Visit (Study Day 14)

- Investigators will solicit any adverse events from the patient and/or caregiver and assess
- Vital signs
 - EKG, Blood and urine samples for PK analysis (Assigned Dosage Group patients only)

- Blood and urine samples for safety analysis (Assigned Dosage Group patients only)
- assessments will be performed, including: ABC, SRS, RBS-R, CGI-S, and CGI-I
- Question caregiver or patient about the patient's week, including questions regarding any changes in home life activities, events at school, sleep, or other matters germane to an understanding of the patient's autistic presentation
- Dispense 2 weeks of medication
- Confirmation of medication administration and the collection, counting and logging of unused medicine.
- Record concomitant medications
- Record all adverse events

5.9.2.5 Week 3 Visit (Study Day 21)

- Vital signs
- EKG, Blood and urine samples for PK analysis (Assigned Dosage Group patients only)
- Blood and urine samples for safety analysis (Assigned Dosage Group patients only)
- ASD assessments will be performed, including: ABC, SRS, RBS-R, CGI-S, and CGI-I
- Question caregiver or patient about the patient's week, including questions regarding any changes in home life activities, events at school, sleep, or other matters germane to an understanding of the patient's autistic presentation.
- Confirmation of medication administration
- Record concomitant medications
- Record all adverse events

5.9.2.6 Week 4 Visit (Study Day 28)

- ADOS (all patients) – to be performed during the last week of dosing while patients are still on medication
- Investigators will solicit any adverse events from the patient and/or caregiver and assess
- vital signs
- EKG, Blood and urine samples for PK analysis (Assigned Dosage Group patients only)
- Blood and urine samples for safety analysis for all patients
- Blood drawn for plasma for laboratory studies and for storage
- ASD assessments will be performed, including: ABC, SRS, RBS-R, VABS, CGI-S and CGI-I
- Question caregiver or patient about the patient's week, including questions regarding any changes in home life activities, events at school, sleep, or other matters germane to an understanding of the patient's autistic
- Record concomitant medications
- Record all adverse events

- Confirmation of medication administration and the collection, counting and logging of unused medicine

5.9.2.7 Week 4-5 (Study days 28-35; within 1 week after last dosing)

- Week 1 follow up for Assigned Dosage Group patients only
 - EKG
 - Physical exam with vital signs
 - Hematology
 - Urinalysis
 - Serum chemistry
 - Blood draw for storage
 - ASD assessments will be performed, including: ABC, SRS, RBS-R, CGI-S SAS, VAB II, and CGI-I
 - Record all adverse events
 - Question caregiver or patient about the patient's week, including questions regarding any changes in home life activities, events at school, sleep, or other matters germane to an understanding of the patient's autistic
 - Record concomitant medications

5.9.2.8 Week 8 Follow-Up Visit (Study Day 56)

All patients are to receive:

- Physical exam with vital signs
- Hematology
- Urinalysis
- Serum chemistry
- Blood draw for storage
- ASD assessments will be performed, including: ABC, SRS, RBS-R, CGI-S SAS, VAB II, and CGI-I
- Record all adverse events
- Physical exam with vital signs
 - Question caregiver or patient about the patient's week, including questions regarding any changes in home life activities, events at school, sleep, or other matters germane to an understanding of the patient's autistic
 - Record concomitant medications

5.9.3 PATIENTS IN THE ASSIGNED DOSAGE GROUPS

5.9.3.1 Pharmacokinetic Assessments and Sample Handling

In addition to all of the measures listed above, patients in the Assigned Dosage Groups will provide blood at baseline and at each weekly visit to assess the levels of L1-79 for the purpose of understanding the pharmacodynamic profile of t.i.d. L1-79 administration at the specified doses. Similarly, a 24 urine sample will be collected at every visit at which blood samples are collected for PK analysis, treatment visits Weeks 1 through 4.

Blood samples will be drawn, spun down and frozen for shipment to CMIC for assay. 10 a 10 ml aliquots of blood and urine will for pharmacokinetic assay.

Sample collection methods are presented in [Appendix D](#).

5.9.3.2 Electrocardiograms

Patients in the assigned group will receive EKG as specified in section [5.5.2](#). In the event any EKG abnormalities are noted, additional EKG may be required as described in section [5.5.2](#).

5.9.3.3 1-week Follow-up visit

- At the request of the FDA, patients in the assigned dosage groups will be followed for at one week while continuing to receive their assigned dose of L1-79 t.i.d. in order to assess the safety parameters described herein before submitting a report describing the results of the safety testing, PK/PD results, and EKG to the FDA for their assessment. For the 100 mg t.i.d. group a favorable review of this report is required to enroll the 200 mg t.i.d. dosage group.

